1. REPORTING & ANALYSIS PLAN SYNOPSIS

Overview	Key Elements of the RAP
Purpose	
 The purpose of this reporting and analysis plan (RAP) is to describe the analyses to be included in the CSR for study 200363
Protocol	
 This RAP is based on protocol amendment 4 for study 200363 (GSK Document Number: 2014N216964_04) dated 05/MAY/2016 and the latest version of the electronic Case Report Form (eCRF) [eCRF Version 4.0]. The study protocol consists of two study parts with each study part to be reported sequentially: 
 Pharmacokinetic/Pharmacodynamic Phase (Part A) Long-Term Safety / Long-Term Pharmacodynamic Phase (Part B)
Primary Objectives	
Part A:
 
 To characterize the pharmacokinetics of mepolizumab administered subcutaneously to subjects aged 6 to 11 years old with severe eosinophilic asthma To characterize the pharmacodynamics of mepolizumab administered subcutaneously to subjects aged 6 to 11 years old with severe eosinophilic asthma 
Part B:
 
 To assess the long-term (52 weeks) safety and tolerability of mepolizumab when administered subcutaneously to subjects aged 6 to 11 years old with severe eosinophilic asthma
Primary Endpoints	
Part A:
 
 Population-PK model derived estimates of clearance, area under the plasma-concentration time curve (AUC(0-inf)), maximum plasma concentration (C_{max}), and terminal phase elimination half-life (t_{1/2}) of mepolizumab Change from baseline in blood eosinophil count at week 12 
Part B:
 
 Incidence of Adverse Events Frequency of positive anti-mepolizumab binding antibodies and neutralizing antibodies Incidence of clinically significant changes in vital sign measurements Incidence of clinically significant changes in clinical laboratory parameters
Secondary Objectives	
Part A:
 
 To compare the bodyweight-adjusted clearance between adults and subjects aged 6 to 11 years old with severe eosinophilic asthma when mepolizumab is administered subcutaneously To characterize asthma control following subcutaneous administration of mepolizumab to subjects aged 6 to 11 years old with severe eosinophilic asthma To assess the safety and tolerability of mepolizumab when administered subcutaneously to subjects aged 6 to 11 years old with

Overview	Key Elements of the RAP
	
severe eosinophilic asthma
 
Part B:
 
 • To characterize the long-term (52 weeks) durability of pharmacodynamics of mepolizumab administered subcutaneously to subjects aged 6 to 11 years old with severe eosinophilic asthma
Secondary Endpoints	
Part A:
 
 • Bodyweight-adjusted clearance estimates obtained by population PK methods. • Change from Baseline in ACQ-7 measured at week 12 • Change from Baseline in ACQ-7 measured at week 4,8,16 and 20 • Change from Baseline in C-ACT measured at week 12 • Change from Baseline in C-ACT measured at week 4,8, 16 and 20 • Incidence of Adverse Events (AEs) • Incidence of clinically significant changes in clinical laboratory parameters • Frequency of positive anti-mepolizumab binding antibodies and neutralizing antibodies • Incidence of clinically significant changes in vital sign measurements 
Part B:
 
 • Change from Baseline in absolute blood eosinophil count at weeks 32, 44, 56, 68, 72 and 80.
Study Design	
Part A:
 
 • This is a multi-centre, open-label study that will assess the pharmacokinetics and pharmacodynamics of three 4-weekly doses of mepolizumab, either 40 or 100mg SC depending on subject bodyweight, administered subcutaneously to subjects with severe eosinophilic asthma aged 6-11 years. • Approximately 40 male or female subjects with severe eosinophilic asthma, aged 6 to 11 years inclusive at screening (Visit 1), will be screened to achieve approximately 28 eligible subjects entering the treatment phase to allow availability of 20 evaluable subjects; with a minimum of six subjects enrolled in the < 40 kg bodyweight group. An evaluable subject is defined to be a subject who has received all three doses of mepolizumab and has had all PK and PD assessments completed through to Visit 6 (week 12). 
Part B:
 
 • This is a long-term safety / pharmacodynamic phase in which extended treatment for a further 52 weeks will be offered on an optional basis to those subjects eligible for continued treatment. Subjects will receive either 40 or 100mg depending on subject bodyweight, administered SC every 4 weeks to subjects with severe eosinophilic asthma aged 6-11 years. At the end of the 52 weeks extended treatment in Part B, subjects will have an Exit Visit 4 weeks after last dose and a Follow-Up visit 12 weeks after last dose. • All subjects who completed Part A and meet the eligibility criteria for Part B will be allowed to participate in Part B.

Overview	Key Elements of the RAP
Planned Analyses	
Part A:
 
 A complete analysis of part A for an interim report in accordance with all Part A study objectives and endpoints will be performed after all subjects have completed Part A of the study. All outputs will be considered the final analyses for Part A. 
Part B:
 
 A complete analysis of part B for a final report in accordance with all Part B study objectives and endpoints will be performed after all subjects have completed Part B of the study.
Analysis Populations	
Part A:
 
 All Subjects Enrolled (ASE): All subjects for whom a record exists on the study database. Safety Population: All subjects receiving at least one dose of mepolizumab beginning at Visit 2. Pharmacokinetic (PK) Population: All subjects receiving at least one dose of mepolizumab beginning at Visit 2 and having at least one blood sample taken at Visit 3 or thereafter with measurable mepolizumab plasma concentration. Pharmacodynamic (Blood Eosinophils) (PDe) Population: All subjects receiving at least one dose of mepolizumab beginning at Visit 2 and having at least one Part A blood sample taken for blood eosinophil count. Pharmacodynamic (Outcome Assessments) (PDo) Population: All subjects receiving at least one dose of mepolizumab beginning at Visit 2 and having at least one Part A assessment of pharmacodynamic outcomes (ACQ-7, C-ACT, asthma exacerbation, FEV₁, IgE or IL-5). Pharmacokinetic / Pharmacodynamic (PKPD) : All subjects receiving at least one dose of mepolizumab beginning at Visit 2 and having at least one blood sample taken at Visit 3 or thereafter with measurable mepolizumab plasma concentration and who also have a baseline PDe measurement and at least one post-treatment PDe measurement. 
Part B:
 
 Safety Population: All subjects receiving at least one dose of study medication beginning at Visit 9. Pharmacodynamic (Blood Eosinophils) (PDe) Population: All subjects receiving at least one dose of mepolizumab beginning at Visit 9 and having at least one Part B one blood sample taken for blood eosinophil count. Pharmacodynamic (Outcome Assessments) (PDo) Population: All subjects receiving at least one dose of mepolizumab beginning at Visit 9 and having at least one Part B assessment of pharmacodynamic outcomes (ACQ-7, C-ACT, asthma exacerbation, or FEV₁).

Overview	Key Elements of the RAP
Hypothesis	
 Formal hypothesis testing will not be performed for this study. An estimation approach will be adopted to evaluate the objectives.
Primary Analyses	
Part A:
 
 PK samples will be analysed by population-PK methods based on the PK population. A number of pharmacokinetic parameters will be fixed from adult values in the model in support of the sparse sampling implemented in the study and the relatively small sample size. In particular meaningful estimation of absorption and distribution parameters is unlikely based on the sampling scheme. The population-PK parameter estimates (AUC(0-inf), clearance, C_{max} and t_{1/2}) with 95% confidence intervals from the final model will be tabulated. In addition, the individual PK parameter estimates (also called post-hoc individual PK parameter estimates) (AUC(0-inf), clearance, C_{max} and t_{1/2}) will be summarised including 95% CIs. The absolute blood eosinophil count and ratio of blood eosinophil count to baseline will be summarised using summary statistics including 95% CIs, for all post-dosing study visits. 
Part B:
 
 Safety data including adverse events, vital signs, clinical laboratory, electrocardiogram (ECG), and immunogenicity data will be summarised.
Secondary Analyses	
Part A:
 
 Bodyweight-adjusted clearance in this study from subjects aged 6 to 11 years old will be compared with historical values from adults with severe eosinophilic asthma when mepolizumab is administered subcutaneously. For this purpose, the bodyweight-adjusted clearance obtained from the population PK model of data from this study will be presented in a separate table with 90% CI. This point estimate and 90% CI will be compared with the historic value in adults of 0.22 L/day (corresponding to an apparent clearance of 0.29 L/day assuming an absolute bioavailability of 75%), around which a proposed 80-125% interval was applied (i.e., 0.18-0.28 L/day). Change from baseline in the overall ACQ-7 and C-ACT score will be summarised including 95% CIs. In addition the proportion of subjects meeting the minimally clinically significant change (reduction from baseline of ≥ 0.5 in the overall ACQ-7 score) will be presented. 
Part B:
 
 The absolute blood eosinophil count and ratio of blood eosinophil count to baseline will be summarised using summary statistics including 95% CIs, for all post-dosing study visits.
Safety	
 Safety data including adverse events, vital signs, clinical laboratory, electrocardiogram (ECG), and immunogenicity data will be summarised.

2. SUMMARY OF KEY PROTOCOL INFORMATION

The study protocol consists of two study parts which are to be reported sequentially:

- Pharmacokinetic/Pharmacodynamic Phase (Part A)
- Long-Term Safety / Long-Term Pharmacodynamic Phase (Part B)

2.1. Changes to the Protocol Defined Statistical Analysis Plan

Any changes from the originally planned statistical analysis specified in the protocol amendment 4 (dated 05/MAY/2016) are outlined in [Table 1](#).

Table 1 Changes to Protocol Defined Analysis Plan

Protocol	Reporting & Analysis Plan	
Statistical Analysis Plan	Statistical Analysis Plan	Rationale for Changes

 • Part B endpoint listed as 'Change from Week 20 (Visit 9) in absolute blood eosinophil count at weeks 32, 44, 56, 68, 72 and 80' 	
 • Part B endpoint listed as 'Change from Baseline in absolute blood eosinophil count at weeks 32, 44, 56, 68, 72 and 80' 	
 • Patients will not have returned to their pre-mepolizumab treatment baseline at the start of part B [Week 20 (Visit 9)] and therefore individual patient comparisons back to Baseline (Week 0) are more of interest

 • Part B endpoint listed as 'Change from Week 20 (Visit 9) in ACQ-7 and C-ACT at weeks 32, 44, 56, 68, 72 and 80.' 	
 • Part B endpoint listed as 'Change from Baseline in ACQ-7 and C-ACT at weeks 32, 44, 56, 68, 72 and 80.' 	
 • Patients will not have returned to their pre-mepolizumab treatment baseline at the start of part B [Week 20 (Visit 9)] and therefore individual patient comparisons back to Baseline (Week 0) are more of interest

2.2. Study Objective(s) and Endpoint(s)

2.2.1. Pharmacokinetic/Pharmacodynamic Phase (Part A)

Objectives	Endpoints
Primary	

 • To characterize the pharmacokinetics of mepolizumab administered subcutaneously to subjects aged 6 to 11 years old with severe eosinophilic asthma • To characterize the pharmacodynamics of mepolizumab administered subcutaneously to subjects aged 6 to 11 years old with severe eosinophilic asthma 	
Population-PK model derived estimates of clearance, area under the plasma-concentration time curve (AUC(0-inf), maximum plasma concentration (C_{max}), and terminal phase elimination half-life (t_{1/2}) of mepolizumab
 
 • Change from baseline in blood eosinophil count at week 12

Objectives	Endpoints
Secondary	

 • To compare the bodyweight-adjusted clearance between adults and subjects aged 6 to 11 years old with severe eosinophilic asthma when mepolizumab is administered subcutaneously • To characterize asthma control following subcutaneous administration of mepolizumab to subjects aged 6 to 11 years old with severe eosinophilic asthma • To assess the safety and tolerability of mepolizumab when administered subcutaneously to subjects aged 6 to 11 years old with severe eosinophilic asthma 	
 • Bodyweight-adjusted clearance estimates obtained by population PK methods. • Change from Baseline in ACQ-7 measured at week 12 • Change from Baseline in ACQ-7 measured at weeks 4,8, 16 and 20 • Change from Baseline in C-ACT measured at week 12 • Change from Baseline in C-ACT measured at week 4, 8, 16 and 20 • Incidence of Adverse Events • Incidence of clinically significant changes in clinical laboratory parameters • Frequency of positive anti-mepolizumab binding antibodies and neutralizing antibodies • Incidence of clinically significant changes in vital sign measurements
Exploratory	

 • To assess the number of asthma exacerbations that occur during the study following subcutaneous administration of mepolizumab to subjects aged 6 to 11 years old with severe eosinophilic asthma • To assess Forced expiratory volume in 1 second (FEV1) following subcutaneous administration of mepolizumab to subjects aged 6 to 11 years old with severe eosinophilic asthma 	
 • Number of asthma exacerbations that occur while on treatment (week 0-week 12). • Number of asthma exacerbations that occur on- treatment and post-treatment (week 0 – week 20) • Change from Baseline in FEV1 measured at week 12

2.2.2. Long-Term Safety/Long-Term Pharmacodynamic Phase (Part B)

Objectives	Endpoints
Primary	

To assess the long-term (52 weeks) safety and tolerability of mepolizumab when administered subcutaneously to subjects aged 6 to 11 years old with severe eosinophilic asthma
	
 • Incidence of Adverse Events • Frequency of positive anti-mepolizumab binding antibodies and neutralizing antibodies • Incidence of clinically significant changes in vital sign measurements • Incidence of clinically significant changes in clinical laboratory parameters
Secondary	

 • To characterize the long-term (52 weeks) durability of pharmacodynamics of mepolizumab administered subcutaneously to subjects aged 6 to 11 years old with severe eosinophilic asthma 	
 • Change from Baseline in absolute blood eosinophil count at weeks 32, 44, 56, 68, 72 and 80.
Exploratory	

 • To assess the number of asthma exacerbations that occur during the long-term (52 weeks) part of the study following subcutaneous administration of mepolizumab to subjects aged 6 to 11 years old with severe eosinophilic asthma • To characterize the long-term (52 weeks) asthma control following subcutaneous administration of mepolizumab to subjects aged 6 to 11 years old with severe eosinophilic asthma 	
 • Incidence of asthma exacerbations • Change from Baseline in ACQ-7 and C-ACT at weeks 32, 44, 56, 68, 72 and 80.

2.3. Study Design

Overview of Study Design and Key Features	

Part A:
 
■ Mepolizumab [100mg (subjects with body weight ≥ 40 kg) OR 40mg (subjects with body weight < 40 kg)
	
Design Features	
Part A:
 
 This is a multi-centre, open-label study that will assess the pharmacokinetics and pharmacodynamics of three 4-weekly doses of mepolizumab, either 40 or 100mg SC depending on subject bodyweight, administered subcutaneously to subjects with severe eosinophilic asthma aged 6-11 years. Approximately 40 male or female subjects with severe eosinophilic asthma, aged 6 to 11 years inclusive at screening (Visit 1), will be screened to achieve approximately 28 eligible subjects entering the treatment phase to allow availability of 20 evaluable subjects; with a minimum of six subjects enrolled in the < 40 kg bodyweight group. An evaluable subject is defined to be a subject who has received all three doses of mepolizumab and has had all PK and PD assessments completed through to Visit 6 (week 12). 
Part B:
 
 This is a long-term safety / pharmacodynamic phase in which extended treatment for a further 52 weeks will be offered on an optional basis to those subjects eligible for continued treatment. Subjects will receive either 40 or 100mg depending on subject bodyweight, administered SC every 4 weeks to subjects with severe eosinophilic asthma aged 6-11 years. At the end of the 52 weeks extended treatment in Part B, subjects will have an Exit Visit 4 weeks after last dose and a Follow-Up visit 12 weeks after last dose. All subjects who completed Part A and meet the eligibility criteria for Part B will be allowed to participate in Part B. Countries participating in this study include: Japan, Poland, United States and United Kingdom.
Dosing	
Part A:
 
 Mepolizumab will be administered as either 40mg (subjects < 40kg at

Overview of Study Design and Key Features	
	
Visit 2) or 100 mg SC (subjects ≥ 40kg at Visit 2) at week 0 (Visit 2), week 4 (Visit 3) and week 8 (Visit 4) which will provide therapeutic coverage through to week 12 (Visit 6). The mepolizumab dose received throughout Part A will remain unchanged irrespective of bodyweight changes.
 
Part B:
 
 • Within Part B the subject's dose will be adjusted to 100mg SC from the time the subject's bodyweight reaches 40 kg. Subjects will receive either mepolizumab 40 or 100 mg SC, (depending on subject bodyweight measured at Visit 9; 40 mg for subjects < 40 kg and 100 mg for subjects ≥ 40 kg). Subjects with bodyweight < 40 kg at Visit 9 should be weighed at each subsequent visit and have their dose adjusted to 100mg once their bodyweight reaches 40 kg. Subjects weighing ≥ 40kg at Visit 9 will receive the 100mg dose at all subsequent treatment visits and will not be weighed again.
Planned Analyses	
Part A:
 
 • A complete analysis of part A for an interim report in accordance with all Part A study objectives and endpoints will be performed after all subjects have completed Part A of the study. All outputs will be considered the final analyses for Part A. 
Part B:
 
 • A complete analysis of part B for a final report in accordance with all Part B study objectives and endpoints will be performed after all subjects have completed Part B of the study.

2.4. Statistical Hypotheses

Formal hypothesis testing will not be performed for this study. An estimation approach will be adopted to evaluate the objectives.

3. PLANNED ANALYSES

3.1. Part A Analysis

A complete analysis of part A for an interim report in accordance with all Part A study objectives and endpoints will be performed after all subjects have completed Part A of the study and after the completion of the following sequential steps detailed below.

All outputs will be considered the final analyses for Part A

1. All subjects have completed Part A (upon completion of all study procedures or premature discontinuation of the study) as defined in the protocol for study 200363.
2. All required database cleaning activities have been completed and database release and database freeze has been declared by Data Management.

3.2. Part B Analysis

A complete analysis of part B for a final report in accordance with all Part B study objectives and endpoints after all subjects have completed Part B of the study. The database will be locked after all subjects have completed all Part B assessments and the required database cleaning activities have been completed. Once this has been achieved the database will be frozen. Statistical outputs generated following the interim report (Part A) will not be reproduced.

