9.3.2. Interim Analysis

A full interim analysis is planned at the completion of the Pharmacokinetic/Pharmacodynamic Phase (Part A) of this study. All eCRF data will be monitored, queried, and a soft-database lock will be performed on all subject data through Visit 8 following last subject achieving Visit 8. A statistical output will be prepared in accordance with all study objectives and endpoints for Part A.

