- The investigator is obligated to perform or arrange for the conduct of supplemental measurements and/or evaluations as may be indicated or as requested by GSK to elucidate as fully as possible the nature and/or causality of the AE or SAE.
- The investigator is obligated to assist. This may include additional laboratory tests or investigations, histopathological examinations or consultation with other health care professionals.
- If a subject dies during participation in the study or during a recognized follow-up period, the investigator will provide GSK with a copy of any post-mortem findings, including histopathology.
- New or updated information will be recorded in the originally completed CRF.
- The investigator will submit any updated SAE data to GSK within the designated reporting time frames.

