8.2. Safety Analyses

8.2.1. Overview of Planned Adverse Event Analyses

Safety analyses will be based on the Safety population unless otherwise specified in [Appendix 10: List of Data Displays](#). The safety displays to be created as part of the RAP include all the required and relevant displays identified as per the RAP Core Safety Reporting Template Version 1.0.

[Table 8](#) provides an overview of the planned analyses, with further details of data displays being presented in [Appendix 10: List of Data Displays](#). The same displays will be produced for both study Part A and study Part B data.

Adverse events will be coded using the latest version of the Medical Dictionary for Regulatory Activities (MedDRA).

Table 8 Overview of Planned Adverse Event Analyses

Endpoint	Absolute			
	Summary		Individual	
	T	F	F	L
Exposure				
Number of treatments administered and time on-treatment	Y			Y
Adverse Event				
Overview of Adverse Events	Y			
AEs by SOC and Maximum Intensity	Y			Y
On-Treatment AEs by Overall Frequency	Y			
All Drug-Related AEs by SOC and Maximum Intensity	Y			
Number of subjects & occurrences of common non-serious AEs ^[1] by SOC and PT	Y			
Subject Numbers for Individual AEs				Y
Relationship between AE SOCs, PT & verbatim text				Y
AEs by Highest Antidrug Antibody Result At Any Time Post Baseline	Y			
Serious and Other Significant AEs				
Fatal Serious AEs	Y			Y
Non-Fatal Serious AEs	Y			Y
Reasons for Considering as a Serious Adverse Event				Y
Serious AEs by SOC	Y			
Drug-Related Serious AEs by SOC and Maximum Intensity	Y			
AEs leading to Permanent Discontinuation of Study Treatment or Withdrawal from Study by Overall Frequency	Y			Y
Number of Subjects and Occurrences of Serious, Drug-Related Serious, Fatal Serious, and Drug-Related Fatal Serious AEs	Y			
AEs of Special Interest (On-Treatment) ^[2]				
Systemic Reactions (Hypersensitivity and Non-Allergic)	Y			Y
Local Injection Site Reactions	Y			Y
AEs meeting Anaphylaxis Criteria	Y			Y
Serious Cardiac, Vascular and Thromboembolic (CVT) AEs	Y			Y
Serious Ischemic AEs	Y			Y
Malignancies	Y			Y
Opportunistic Infections	Y			Y
Cardiovascular Events				
All Cardiovascular Events	Y			Y

NOTES :

- T = Table, F = Figure, L = Listing, Y = Yes display generated. PT = Preferred Term, SOC = System Organ Class
- Summary = Represents TFL related to any summaries (i.e. descriptive statistics) of the observed raw data.

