10.5.2. Baseline Definition & Derivations**10.5.2.1. Definition of Baseline**

- The baseline value for each assessment will be the latest value recorded prior to the first dose of mepolizumab.
- If an assessment was performed on the same day as the first dose of study treatment but it is known that the assessment was done after administration of treatment (i.e. because time of assessment is available and is after time of first dose) then this value will not be used as the baseline value.
- The same baseline definition (latest value recorded prior to the first dose of mepolizumab in Part A) will be used in the analyses of both Part A and Part B data.

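### SAP 3.2 rules out re-running Part A outputs, so later updates to Part A adverse events reach no adverse-event table, and a corrected Week 0 value would leave the two reports on different baselines

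*SAP*

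**What the plan says.** Protocol 9.3.2 plans a full analysis at the end of Part A, for which "a soft-database lock will be performed on all subject data through Visit 8 following last subject achieving Visit 8". SAP 3.1 sets the condition in other words: "All required database cleaning activities have been completed and database release and database freeze has been declared by Data Management". It adds that "All outputs will be considered the final analyses for Part A".

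SAP 10.3.1 places both parts in a single study database. Under SAP 3.2 the final lock comes later: "The database will be locked after all subjects have completed all Part B assessments and the required database cleaning activities have been completed". The same section ends with "Statistical outputs generated following the interim report (Part A) will not be reproduced", and gives no exception.

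The protocol expects adverse-event records to go on changing. Section 7.2.1.5 has investigators follow serious events and non-serious events of special interest until they resolve, stabilise or are otherwise explained, or the child is lost to follow-up. Section 12.3.5 lets the investigator revise causality in light of follow-up and says: "New or updated information will be recorded in the originally completed CRF". Section 12.3.6 takes the electronic system off-line only once the study is completed at a site.

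SAP 10.4.1 classifies adverse events by onset relative to dosing in each part. On baseline, SAP 10.5.2.1 says the last value before the first Part A dose "will be used in the analyses of both Part A and Part B data".

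**The concern.** Cleaning before the Part A freeze deals with errors present at that time. It does not deal with new facts about an event correctly recorded at the freeze, and these are what the protocol asks sites to keep adding. If such a fact arrives after the freeze, the Part A tables are not re-run, and the Part B tables exclude the event because its onset lies in Part A. A child who never enters Part B has no Part B display at all. Entry requires all three Part A doses and completed assessments through Visit 8 (protocol 5.3), so this includes any child who stopped Part A early because of an adverse event.

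At stake are the Part A counts of serious, drug-related and severe events. Adverse-event incidence is a secondary endpoint in Part A. There is also a consistency problem: the Part A and Part B eosinophil ratios share one baseline by definition, but would be computed from it at two different times.

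**Working it through.** **1. Length of the exposed period.** Protocol section 4 gives Part B as approximately 60 weeks, or 52 for children moving to the access program. From the visit schedule, with Visit 9 on the same day as Visit 8 (Week 20):
- to Visit 23: 80 − 20 = 60 weeks = 420/365.25 = 1.15 years;
- to Visit 22: 72 − 20 = 52 weeks = 364/365.25 = 1.00 year.

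The protocol's figures are reproduced. With the ±5-day window the extremes are (364 − 5)/7 = 51.3 and (420 + 5)/7 = 60.7 weeks. The period runs from the common Part A cut, not from each child's own Visit 8. It reaches 52 to 60 weeks only if one of the last children to finish Part A enters Part B. Enrolment timing and cleaning time are not given.

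**2. Where an updated Part A event would appear.** Take a hypothetical event with onset at Week 18 in a child who continues. It is non-serious at the freeze and becomes serious afterwards.
- Part A post-treatment runs from the last Part A dose + 28 days (Week 8 + 4 = Week 12) to the first Part B dose (Week 20). The event belongs here.
- At the freeze it enters the Part A post-treatment tables (3.5, 3.6) as non-serious. The serious-event tables (3.15, 3.17) were produced without it and are not re-run.
- Part B on-treatment starts at the first Part B dose (Week 20), so Tables 3.67 and 3.69 exclude it.
- Part B post-treatment starts more than 28 days after the last Part B dose, so Tables 3.68 and 3.70 exclude it.

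Its serious status is therefore in no adverse-event table. The same holds for revised causality (Tables 3.8, 3.9, 3.18, 3.19), revised intensity (3.4, 3.6, 3.9) and revised outcome (the special-interest profile tables).

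**3. Sensitivity of a count.** About 28 children are to be dosed, with at least six in the <40 kg group (protocol 4.3).
- One child moving category: 1/28 = 3.6 percentage points overall.
- In a group of six: 1/6 = 16.7 points.

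These are step sizes, not expected errors. They apply only if the child has no other event in that category.

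**4. Baseline.** Suppose one child's Week 0 eosinophil count is corrected by a factor f. That child's ratio to baseline is divided by f, and the geometric mean ratio over n children is multiplied by f^(−1/n). The values of f are assumed.

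| f | n = 20 | n = 28 |
|---|---|---|
| 1.5 | 0.980 | 0.986 |
| 2 | 0.966 | 0.976 |
| 10 | 0.891 | 0.921 |

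At the ratio of 0.14 used as the example in protocol 9.2, with n = 20, f = 2 gives 0.14 × 0.966 = 0.135 and f = 10 gives 0.14 × 0.891 = 0.125. Both lie well inside the interval of 0.09 to 0.20 that the plan expects. The Part A table would keep 0.14. The Part B tables would use the corrected baseline, with a shift that depends on how many children enter Part B, which is not fixed.

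**The case against.** The strongest reply is that sequential reporting is the declared design and is properly controlled. SAP 3.1 requires completed cleaning, release and a declared freeze before any Part A output. SAP 10.3.2 defines the data cut and documents the removal of later data. Neither document says that Part A records remain editable after the freeze. Mandatory follow-up to resolution covers only serious and special-interest events, and the cut falls after Visit 8, 12 weeks after the last dose. A later resolution date changes no system-organ-class count. Part A safety is descriptive and no hypothesis is tested. Re-running everything would mean 99 tables, 25 figures and 51 listings, some supplied by a separate modelling group.

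Much of this stands. The term soft lock taken alone understates the control, and post-freeze editing is partly an inference. The inference is a strong one, because the protocol directs updates into the existing record and keeps the electronic system available until the site has completed the study. The reply does not meet the main point: the no-re-run rule is unconditional, and a genuine change to a Part A event has no later table.

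A reader might infer three stronger things that the documents do not support:
- **Corrected baselines reach no table.** For children who continue, they do. SAP 8.1.4 and 10.5.2.1 carry the same Week 0 value into Part B, and the Part B eosinophil, laboratory, ECG and vital-sign tables use it. The risk is disagreement between the two reports.
- **A change of MedDRA version between the reports distorts a comparison.** SAP 8.2.1 calls for the latest version, so the versions may differ, but no planned table pools or compares adverse events across the parts.
- **Every Part A display must be re-run and recoded.** Recoding alone could move preferred-term counts with no change in the data. That would add differences rather than remove them.

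**Conclusion.** The point holds, limited to two consequences. First, a Part A-onset adverse event whose seriousness, causality, intensity or outcome is updated after the Part A freeze appears with its final status in no adverse-event table of either report. Second, a corrected Week 0 value would change Part B ratios but not the Part A ratio, so the two reports could show different baselines for the same child.

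This is a stated rule that can leave a wrong safety count standing, not merely a missing detail. It rests on two assumptions: that Part A records can be updated after the freeze, and that at least one relevant update occurs. Neither document gives a rate for the second, so the 3.6-point and 16.7-point steps must not be read as a likely error. The baseline effect is small unless the correction is gross. Nothing here shows that the primary PK or eosinophil conclusion would be wrong. The change is worth making because it is cheap and because the rule works against follow-up that the protocol itself requires.

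**What to change.** Replace the last sentence of SAP 3.2 with text to this effect:

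*Part A data at the Part A freeze will be compared electronically with the final locked database. Every change to a Part A record will be listed with its reason in the final report. Any Part A display whose values are affected will be re-run and reported alongside the interim value. The population PK model will be refitted only if a concentration, dose time or bodyweight changed. The MedDRA version used for each report will be stated.*

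It would also help to use one term for the Part A data state in protocol 9.3.2 and SAP 3.1, and to say what edits it allows.

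The cost is a data comparison and a small amount of programming. A few Part A figures may differ from the interim report and need a short explanation. If nothing has changed, the comparison records that and no display is re-run. One limit remains: under protocol 12.3.6, updates that arrive after a site's electronic system is off-line come on paper or by telephone, and the comparison sees only what reaches the database.
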